## PROTOCOL AMENDMENT

**Protocol Number:** ION-827359-CS2**Protocol Title:** A Double-Blind, Placebo-Controlled, Phase 2a Study to Assess the Safety, Tolerability, and Efficacy of ION-827359 in Patients with Mild to Moderate COPD with Chronic Bronchitis**Amendment Number:** 3**Amendment Date:** 2 February 2021

The major purpose of this amendment is to help prevent any potential bronchospasm after inhalation of Study Drug.

A list of changes to the protocol are below:

Protocol Section	Description of Change	Rationale
Section 6.1.3 Treatment Period	
The following is deleted from Table 1 (Withhold times for bronchodilators):
 
LABA (e.g., formoterol or salmeterol) 24 hours Ultra-LABA (e.g., indacaterol, vilanterol, or olodaterol) 36 hours LAMA (e.g., tiotropium, umeclidinium, aclidinium, or glycopyrronium) 36 – 48 hours
 
The following is added:
 
The usual dose of bronchodilators should not be taken the morning of the visit, until after spirometry is performed and prior to dosing (if applicable) with the study medication. Albuterol (salbutamol) 2 puffs, should be dosed prior to study drug both for in-clinic and at-home dosing.
	To help prevent any potential bronchospasm
Appendix A Schedule of Procedures	
Footnote 2 (vital signs) currently reads:
 
 BP, heart rate (HR), respiratory rate (RR), temperature
 
Will be amended to:
 
 BP, heart rate (HR), respiratory rate (RR), temperature, and pulse oximetry
	Correct an omission.
Appendix A Schedule of Procedures	
Footnote g added for spirometry on Day 1:
 
Perform spirometry (pre-Study Drug) pre and 20-30 minutes post albuterol dose (2 puffs) and then perform spirometry 1 and 2 hours post-Study Drug dosing.
	Collect baseline post-albuterol spirometry

## PROTOCOL SYNOPSIS

Protocol Title	A Double-Blind, Placebo-Controlled, Phase 2a Study to Assess the Safety, Tolerability, and Efficacy of ION-827359 in Patients with Mild to Moderate COPD with Chronic Bronchitis
Study Phase	2a
Indication	Chronic Bronchitis (CB)
Primary Objective	To evaluate the efficacy of ION-827359 in patients with mild to moderate CB over 13 weeks of treatment
Secondary Objectives	

• To evaluate the effect of ION-827359 on symptoms of CB

• To evaluate the effect of ION-827359 on quality of life (QoL) in COPD patients with CB

• To evaluate the pharmacokinetics of ION-827359 in COPD patients with CB

• To evaluate the safety and tolerability of ION-827359 compared to placebo

Exploratory Objectives	

• To assess changes in lung volumes (RV, FRC)

• To assess changes in lung mucins (total, MUC5AC, and MUC5B)

• To assess changes in regional lung ventilation in low dose high resolution CT scanning (HRCT) scans

• To determine mRNA target engagement and inflammatory biomarkers

• To evaluate the dose response of ION-827359

Study Design	Double-blind, placebo-controlled, multi-center study
Number of Patients	Approximately 180 patients
Study Population	Inclusion Criteria 

1. Must have given written informed consent (signed and dated) and any authorizations required by local law and be able to comply with all study requirements

2. Males or females. Aged 40–70 inclusive at the time of informed consent

3. Females must be non-pregnant and non-lactating, and either surgically sterile (e.g., tubal occlusion, hysterectomy, bilateral salpingectomy, bilateral oophorectomy) or post-menopausal (defined as 12 months of spontaneous amenorrhea without an alternative medical cause and FSH levels in the post-menopausal range for the laboratory involved)

## PROTOCOL SYNOPSIS (Continued)

Study Population (Continued)	Inclusion Criteria Continued
	
Males must be surgically sterile or abstinent*, if engaged in sexual relations with a female of child-bearing potential, the subject must be using a condom in addition to a highly effective contraceptive method by the partner from the time of signing the informed consent form until at least 10 weeks after the last dose of Study Drug (ION-827359 or placebo)
 
* Abstinence is only acceptable as true abstinence, i.e., when this is in line with the preferred and usual lifestyle of the patient. Periodic abstinence (e.g., calendar, ovulation, symptothermal, post-ovulation methods), declaration of abstinence for the duration of a trial and withdrawal are not acceptable methods of contraception
 

4. BMI < 35.0 kg/m^2

5. Patients with a diagnosis of COPD as defined by the American Thoracic Society (ATS)/European Respiratory Society (ERS)

• Ability to perform acceptable and reproducible spirometry

• Post-bronchodilator (4 puffs of albuterol) spirometry at Screening demonstrating the following

• FEV1/FVC ratio of < 0.70

• FEV1 ≥ 50% and ≤ 90% of predicted normal

6. Clinically stable COPD in the 4 weeks prior to Screening (Visit 1)

7. Current and former smokers with smoking history of ≥ 20 pack years

8. Meet SGRQ definition of CB (See Section 6.1.1)

9. CAT score of ≥ 10

 
Exclusion Criteria
 

1. Clinically significant abnormalities in medical history (e.g., previous acute coronary syndrome within 6 months of Screening, major surgery within 3 months of Screening) or physical examination

2. Screening laboratory results as follows, or any other clinically significant abnormalities in screening laboratory values that would render a subject unsuitable for inclusion

• Urine protein/creatinine (P/C) ratio ≥ 0.3 mg/mg. In the event of P/C ratio above this threshold eligibility may be confirmed by a quantitative total urine protein measurement of < 300 mg/24 hr

## PROTOCOL SYNOPSIS (Continued)

Study Population (Continued)	Exclusion Criteria (Continued)
	

• Positive test (including trace) for blood on urinalysis. In the event of a positive test eligibility may be confirmed with urine microscopy showing <math>\leq 5</math> red blood cells per high power field

• ALT, AST, bilirubin, alkaline phosphatase, serum creatinine, BUN <math>> 1.5 \times</math> upper limit of normal (ULN)

• Platelet count <math><</math> LLN

• Serum potassium <math>> 5.2</math> mmol/L

• Estimated GFR <math>< 60</math> mL/min (as determined by the Cockcroft-Gault Equation for creatinine clearance)

3. Any active infection requiring systemic antiviral or antimicrobial therapy that will not be completed prior to Study Day 1

4. Unwillingness to comply with study procedures, including follow-up, as specified by this protocol, or unwillingness to cooperate fully with the Investigator

5. Active infection with human immunodeficiency virus (HIV), hepatitis C or hepatitis B

6. Uncontrolled hypertension (BP <math>> 160/100</math> mm Hg)

7. Malignancy within 5 years, except for basal or squamous cell carcinoma of the skin or carcinoma in situ of the cervix that has been successfully treated. Patients with a history of other malignancies that have been treated with curative intent and which have no recurrence within 5 years may also be eligible if approved by the PI and reviewed by the Sponsor Medical Monitor

8. Treatment with another investigational drug, biological agent, or device within 1 month of Screening, or 5 half-lives of investigational agent, whichever is longer

9. Previous treatment with an oligonucleotide (including siRNA) within 4 months of screening if single dose received, or within 12 months of screening if multiple doses received

10. Clinically important pulmonary disease other than COPD

11. Asthma as a primary or main diagnosis according to the Global Initiative for Asthma (GINA) guidelines (GINA 2011) or other accepted guidelines. Patients with a past medical history of asthma (e.g. childhood or adolescence) may be included

12. Treatment with systemic corticosteroids and/or antibiotics, and/or hospitalization for a COPD exacerbation within 4 weeks prior to enrolment (Visit 1)

## PROTOCOL SYNOPSIS (Continued)

Study Population (Continued)	Exclusion Criteria (Continued)
	

13. Acute upper or lower respiratory infection requiring antibiotics or antiviral medication within 4 weeks prior to enrolment (Visit 1)

14. Long term oxygen therapy (LTOT)

15. Patients participating in, or scheduled for, an intensive (active) COPD rehabilitation program (patients who are in the maintenance phase of a rehabilitation program are eligible to take part)

16. Recent history of, or current drug or alcohol abuse

17. Concomitant medication restrictions: Oral anticoagulants, oral steroids (e.g. prednisone or Medrol), theophylline, chronic azithromycin, or roflumilast

18. Have any other conditions, which, in the opinion of the Investigator would make the subject unsuitable for inclusion, or could interfere with the subject participating in or completing the Study

19. A positive PCR test for SARS-CoV-2 at any time prior to randomization

Treatment Groups	
Patients will be randomized 2:2:1:1 to treatment with:
 

• ION-827359 37.5 mg (1.5 mL) once per week

• ION-827359 75mg (3 mL) once per week

• Placebo (1.5 mL) once per week

• Placebo (3 mL) once per week

Study Drug Dosage and Administration	ION-827359 (25mg/mL) and placebo will be supplied in stoppered glass vials. A total of 1.5 mL or 3 mL will be placed into a Pari eFlow® nebulizer and administered by oral inhalation once weekly.
Study Visit Schedule and Procedures	
Blood and urine samples will be collected regularly throughout the study for safety, PK, and PD analyses. Appendix B shows a list of analytes required for the study. The safety of ION-827359 will be monitored in an ongoing fashion throughout the trial.
 
Screening and Baseline: Study Days -28 to -1
 
Laboratory and other study procedures will be performed to assess eligibility during the Screening Period. Patients will also receive a SARS-CoV-2 PCR test based on nasal/oral swab. Patients will be given an electronic diary to record their baseline daily symptoms starting on Day -7.

[figure not shown]
## PROTOCOL SYNOPSIS (Continued)

Study Visit Schedule and Procedures (Continued)	
Treatment: Study Days 1 to 85
 
Eligible patients will be randomized 2:2:1:1 to ION-827359 (37.5 or 75 mg) or matching placebos. Patients will receive nebulized doses of Study Drug once weekly starting on Study Day 1. Both in-clinic and at-home dosing of ION-827359 will be performed. Patients will record their symptoms in a daily electronic diary and return for study visits to include monitoring and spirometry. There are 3 subset studies:
 

1. A subset of up to about 24 patients will have PK profile sampling performed after the first and last dose

2. A subset of up to about 60 patients will have low dose inspiratory and expiratory HRCT scans to assess regional lung ventilation performed before and post-treatment

3. A subset of up to about 18 patients will undergo bronchoscopy and BAL for target engagement and inflammatory biomarkers before and post-treatment

 
A patient may be enrolled in a maximum of 1 subset study
 
Post-Treatment: Study Days 86 to 162
 
Patients are to return to the Study Center for post-treatment visits on Study Days 92, 120 and 162.
 
Patients that discontinue treatment are encouraged to remain in the study for the Post-Treatment Evaluation Period and will conduct procedures outlined at Study Day 92 visit upon discontinuation of Study Drug.
 
Patients will continue their stable COPD medication regimen throughout the study (screening treatment and post-treatment periods).

Primary Endpoints	Change from Baseline to the primary time point (defined as the average of Weeks 13 and 14) in FEV 1 compared to placebo
Secondary Endpoints	

• Change from Baseline in the E-RS (evaluating respiratory symptoms) daily symptom diary to the primary time point

• Change from Baseline in the CAT to the Week 14 time point

• Change from Baseline in SGRQ to the Week 14 time point

• Change from Baseline in post-bronchodilator FEV1

• Pharmacokinetics

• Incidence and severity of treatment-emergent adverse events (TEAE)

• Abnormal findings in laboratory assessments, ECG, and vital signs

**PROTOCOL SYNOPSIS (Continued)**

Exploratory Endpoints	

• Change from Baseline in sputum mucins (total, MUC5AC, and MUC5B)

• Change from Baseline in ENaC mRNA levels from bronchial brushings

• Change from Baseline in inflammatory biomarkers from bronchoalveolar lavage

• Change from Baseline in FRC (functional respiratory capacity) and RV (residual volume)

• Change from Baseline in regional lung volumes as measured by HRCT

Statistical Considerations	
The sample size assumptions for the primary endpoint include:
 

• The increase in FEV1 from Baseline to the primary time point in the ION-827359 treatment group is 100 mL; no change in the placebo group

• Standard deviation of change in FEV1 is 220 mL

• Significance level (alpha) of 0.05 (2-sided test)

 
With the above assumptions, a sample size of 174 patients (58 patients in each ION-827359 treatment groups and 29 patients in each placebo group) will provide a power of at least 80% for the primary comparison (pooled ION-827359 treatment groups vs. pooled placebo groups). Approximately 180 patients will be enrolled in this trial to account for a 3% dropout rate.

Sponsor	Ionis Pharmaceuticals

## STUDY DESIGN AND TREATMENT SCHEMA

**STUDY GLOSSARY**

Abbreviation	Definition
AE	adverse event
ALP	alkaline phosphatase
ALT	alanine aminotransferase (SGPT)
aPTT	activated partial thromboplastin time
ASO	antisense oligonucleotide
AST	aspartate aminotransferase
ATS	American Thoracic Society
AUC t	area under the plasma concentration-time curve from time zero to time t
BAL	bronchoalveolar lavage
βhCG	beta-subunit of human chorionic gonadotropin (pregnancy test)
BP	blood pressure
BUN	blood urea nitrogen
C	centigrade
C5a	complement factor C5a (activated complement split product)
CAT	COPD assessment test
CB	chronic bronchitis
CL	systemic clearance
CMV	cytomegalovirus
COPD	chronic obstructive pulmonary disease
CS	clinically significant
CT	computed tomography
CTCAE	Common Terminology Criteria for Adverse Events
DL	deciliter
DLCO	diffusing capacity
ECG	electrocardiogram
eCRF	electronic Case Report Form
eGFR	estimated glomerular filtration rate
ENaC	epithelial sodium channel
ERS	European Respiratory Society
E-RS	EXACT respiratory symptoms
FAS	Full Analysis Set
FEV 1	forced expiratory volume in 1 second
FRC	functional residual capacity
FSH	follicle stimulating hormone
FVC	forced vital capacity
g	gram
GCP	Good Clinical Practice
HBsAg	hepatitis B surface antigen
HCV	hepatitis C virus
HIV	human immunodeficiency virus
HRCT	high resolution CT scanning
ICH	International Conference on Harmonization
IEC	Independent Ethics Committee

---

IgM	immunoglobulin M
IL-5	interleukin-5
IL-8	interleukin-8
INR	international normalized ratio
IRB	Institutional Review Board
ION-827359	antisense inhibitor of ENaC
kg	kilogram
m 	square meter
MAD	multiple-ascending dose
MCH	mean corpuscular hemoglobin
MCHC	mean corpuscular hemoglobin concentration
MCV	mean corpuscular volume
MedDRA TM	Medical Dictionary for Regulatory Activities
mg	milligram
mL	milliliter
mm	millimeter
mRNA	messenger ribonucleic acid
NCI	National Cancer Institute
NCS	not clinically significant
NOAEL	no adverse effect level
on study	the patient is ‘on study’ from signing of the informed consent until their last study visit
P/C	urine protein/creatinine
pH	measure of the acidity or basicity of a solution
PK	pharmacokinetic(s)
PPS	Per Protocol Set
PT	prothrombin time
QoL	quality of life
RNase H1	an ubiquitous endonuclease that specifically hydrolyzes the RNA strand in RNA/DNA hybrids
RV	residual volume
SAD	single-ascending dose
SAE	serious adverse event
SAP	Statistical Analysis Plan
SGRQ	St. George’s Respiratory Questionnaire
siRNA	small interfering ribonucleic acid
TLC	total lung capacity
Study Day 1	defined as the first day Study Drug product is administered to the patient
Study Drug	ION-827359 or placebo
SUSAR	suspected unexpected serious adverse reaction
TEAE	treatment-emergent adverse event
T max	time to maximal concentration
ULN	upper limit of normal
WBC	white blood cell
WOCBP	woman of child-bearing potential

## 1. OBJECTIVES AND ENDPOINTS

### 1.1. Objectives

#### 1.1.1. Primary Objective

To evaluate the effect of ION-827359 on forced expiratory volume in 1 second (FEV1) in patients with mild to moderate chronic obstructive pulmonary disease (COPD) with chronic bronchitis (CB)

#### 1.1.2. Secondary Objectives

- To evaluate the effect of ION-827359 on symptoms of CB
- To evaluate the effect of ION-827359 on quality of life (QoL) in patients of CB
- To evaluate the pharmacokinetics (PK) of ION-827359 in patients with CB
- To evaluate the safety and tolerability of ION-827359 compared to placebo

#### 1.1.3. Additional/Exploratory Objectives

- Assess changes in PD markers
- Assess changes in lung volumes
- Assess changes in lung ventilation
- Assess target engagement

## 1.2. Study Endpoints

### 1.2.1. Primary Endpoint

Change from Baseline to the primary time point (defined as the average of Weeks 13 and 14) in FEV1 compared to placebo

#### 1.2.2. Secondary Endpoints

- Change from Baseline in the EXACT respiratory symptoms (E-RS) (evaluating respiratory symptoms) daily symptom diary to the primary time point
- Change from Baseline in the COPD assessment test (CAT) to the Week 14 time point
- Change from Baseline in St. George's Respiratory Questionnaire (SGRQ) to the Week 14 time point
- Change from Baseline in post-bronchodilator FEV1
- Pharmacokinetics (Section 1.2.3.1)
- Safety Endpoints
  - Incidence and severity of treatment-emergent adverse events (TEAE)
  - Abnormal findings in laboratory assessments, electrocardiogram (ECGs), and vital signs

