## 5.2. Exclusion Criteria

1. Clinically significant abnormalities in medical history (e.g., previous acute coronary syndrome within 6 months of screening, congestive heart failure, major surgery within 3 months of Screening) or physical examination
2. Screening laboratory results as follows, or any other clinically significant abnormalities in screening laboratory values that would render a subject unsuitable for inclusion
  - Urine protein/creatinine (P/C) ratio  $\geq 0.3 \text{ mg/mg}$ . In the event of P/C ratio above this threshold eligibility may be confirmed by a quantitative total urine protein measurement of  $< 300 \text{ mg/24 hr}$
  - Positive test (including trace) for blood on urinalysis. In the event of a positive test eligibility may be confirmed with urine microscopy showing  $\leq 5$  red blood cells per high power field
  - alanine aminotransferase (ALT), aspartate aminotransferase (AST), bilirubin, alkaline phosphatase (ALP), serum creatinine, blood urea nitrogen (BUN)  $> 1.5 \times$  upper limit of normal (ULN)
  - Platelet count  $< \text{LLN}$
  - Serum potassium  $> 5.2 \text{ mmol/L}$
  - Estimated GFR  $< 60 \text{ mL/min}$  (as determined by the Cockcroft-Gault Equation for creatinine clearance)
3. Any active infection requiring systemic antiviral or antimicrobial therapy that will not be completed prior to first day Study Drug product is administered to the patient (Study Day 1)

4. Unwillingness to comply with study procedures, including follow-up, as specified by this protocol, or unwillingness to cooperate fully with the Investigator
5. Active infection with human immunodeficiency virus (HIV), hepatitis C or hepatitis B
6. Uncontrolled hypertension (blood pressure (BP) > 160/100 mm Hg)
7. Malignancy within 5 years, except for basal or squamous cell carcinoma of the skin or carcinoma *in situ* of the cervix that has been successfully treated. Patients with a history of other malignancies that have been treated with curative intent and which have no recurrence within 5 years may also be eligible if approved by the PI and reviewed by the Sponsor Medical Monitor
8. Treatment with another investigational drug, biological agent, or device within 1 month of Screening, or 5 half-lives of investigational agent, whichever is longer

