## Appendix A. Schedule of Procedures (Continued)

Study Week/Day	Screen	Run-in Period	Treatment Period (13 Weeks)								Post-Treatment Period (10 Weeks) +		
			W1 D1	W3 D15	W5 D29	W7 D43	W9 D57	W13 D85	W14 D92 (and Early Term)	W15 D99 	W18 D120	W24 D162	
Visit Window (Days)	NA	± 1	NA	± 2	± 3	± 3	± 3	± 2	± 5	± 5	± 5	± 5	
Scheduled Visit Number	1	2	3	4	5	6	7	8	9	9a	10	11	
HRCT scans 	X								X				
Adverse Events	X	X	X	X	X	X	X	X	X	X	X	X	
Concomitant Medications	X	X	X	X	X	X	X	X	X	X	X	X	
PK Blood Sampling 			X a, e	X a	X a		X a	X a, e	X	X	X	X	

Note: If not specifically labeled, "X" means anytime. S, Screening Day, D, Day, W, Week

\* Subjects that terminate early during the Post-Treatment Period should complete all procedures for Study Day 162

+ Post-Treatment Period visits can occur remotely, if necessary.

 Full physical exam to be given at Screening and abbreviated physical exam to be given during Treatment and Follow-up Period as indicated to assess changes from Screening

 BP, heart rate (HR), respiratory rate (RR), temperature, and pulse oximetry

 Women who are not surgically sterile

 For subjects in the bronchoscopy subgroup

 Fasting only for the screening lab. During this time the patient can drink water and they should ensure that they consume sufficient water in order to not become dehydrated

 If the platelet value, serum creatinine or liver enzyme tests are uninterpretable (e.g., due to clumping, hemolysis or quantity not sufficient) or missing a repeat blood specimen should be re-drawn as soon as possible (ideally within 7 days)

 If hematuria or 2+ proteinuria is observed, see confirmation guidance in Section 8.5

 Stored at -80 °C. Can be used for follow-up exploration of laboratory findings and/or AEs (e.g., measurement of cytokine and/or chemokine levels, measurement of additional markers of kidney function, measurement of antibodies, etc.) in this or subsequent clinical studies of ION-827359

 Urine test at Screening. Day 1 can be done at the site using established methods, e.g., a breathalyzer or urine test

 Height at Visit 1 only

 If time is not specified PK draw can be done anytime

 At-home dosing to occur on Days 8, 22, 36, 50, 64, 71, and 78 (± 1 day)

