### **3 ANALYTICAL PLAN**

#### **3.1 General Overview of Analyses**

##### **3.1.1 Statistical Methods**

Descriptive summary statistics including number of subjects, mean, median, standard deviation, standard error, interquartile range (25th percentile, 75th percentile), and range

(minimum, maximum) for continuous variables, and counts and percentages for categorical variables will be used to summarize most data. All statistical tests will be conducted using 2-sided tests with 5% Type I error rate unless otherwise stated. As a Phase 2a study, adjustments for multiplicity of testing will generally not be used.

PK parameters will be summarized using number of Subjects, mean, standard deviation, coefficient of variation (CV), geometric mean, geometric %CV, median, minimum, and maximum.

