### **General Presentation Considerations**

The minimum and maximum will be reported to the same number of decimal places as the raw data recorded in the database. The mean, median, lower quartile and upper quartile will be reported to one more decimal place than the raw data recorded in the database. The standard deviation will be reported to two more decimal places than the raw data recorded in the database. In general, the maximum number of decimal places reported shall be four for any summary statistic.

Categorical data will be summarized in terms of the number of subjects providing data at the relevant time point (n), frequency counts and percentages. Any planned collapsing of categories will be detailed in the text and the data displays.

Percentages will be presented to one decimal place and not be presented for zero counts. Percentages will be calculated using n as the denominator.

P-values greater than or equal to 0.0001, in general, will be presented to four decimal places. P-values less than 0.0001 will be presented as “<0.0001”.

Confidence intervals will be presented to one more decimal place than the raw data.

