**Efficacy/PD Measure Visit Windows**

Measure	Mapped Visit (Week)	Target Day	Study Day Window
Spirometry assessments	1 – 1 hour post dose	1	1
	1 – 2 hours post dose	1	1
	3	15	2-22
	5	29	23 to 36
	7	43	37 to 50
	9	57	51 to 71
	9 – 1 hour post dose	57	51 to 71
	9 – 2 hours post dose	57	51 to 71
	13	85	72 to 88
	14	92	89 to 99
CAT and SGRQ	5	29	2 to 43
	9	57	44 to 74
	14	92	75 to 99
EXACT	2	8	2-8
	3-14	15-99	(Week-1)*7-5 to (Week-1)*7+1
Sputum mucins	5	29	23 to 36

Measure	Mapped Visit (Week)	Target Day	Study Day Window
	7	43	37 to 64
	13	85	65 to 88
	14	92	89 to 99
Plethysmography assessments,	14	92	75 to 99

Data collected under visit labels containing Weeks 18, 24, Days 120 or 162 will not be mapped to analysis week.

Visits after Week 14 are part of the post-treatment assessment period. The efficacy and PD data during the post-treatment period will be summarized using the visit labels provided in the data.

Other data will be summarized using the visit labels provided in the data. Multiple results with the same visit label will be averaged. Results with visit labels as “Unscheduled” will not be included in the by-visit summary tables and figures, but will be included in determining baseline, and in the laboratory abnormality summaries and shift analyses.

All data will be presented in data listings.

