#### **3.4.4 Vital Signs, Weight, and BMI**

Vital signs will include heart rate, respiratory rate, body temperature, systolic and diastolic blood pressure and pulse pressure. Summary tables will be created to present the descriptive statistics for vital sign values, weight, and BMI as well as the change and percent change from baseline at each study visits.

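### Abnormal vital signs are a declared safety endpoint, but no abnormality criterion or patient count is planned, and unscheduled post-baseline readings enter no vital-sign table

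*Combined protocol and SAP*

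**What the plan says.** Protocol 1.2.2 lists under its safety endpoints "Abnormal findings in laboratory assessments, electrocardiogram (ECGs), and vital signs". SAP 1.3.3 repeats this, and the protocol synopsis has the equivalent.

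The planned analysis of the vital-sign part is in SAP 3.4.4: "Summary tables will be created to present the descriptive statistics for vital sign values, weight, and BMI", together with change and percent change from baseline at each visit. Under SAP 3.1.1, descriptive statistics for a continuous variable are the number of subjects, mean, median, standard deviation, standard error, quartiles and range. The presentation rules add: "The minimum and maximum will be reported to the same number of decimal places as the raw data recorded in the database".

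Vital signs are not in the efficacy/PD window table, so they are summarised by the visit label in the data. For such data, SAP 3.1.1 says that results labelled as unscheduled "will not be included in the by-visit summary tables and figures". They still count in determining baseline, in laboratory abnormality summaries and in shift analyses. Several results under one label are averaged. All data are listed.

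The documents also differ on which measurements are vital signs. Protocol Appendix A, footnote 2, collects "BP, heart rate (HR), respiratory rate (RR), temperature, and pulse oximetry". SAP 3.4.4 states: "Vital signs will include heart rate, respiratory rate, body temperature, systolic and diastolic blood pressure and pulse pressure". Pulse oximetry is missing from the SAP list.

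**The concern.** An endpoint worded as abnormal findings asks how many patients had one, by treatment group. That needs a definition of abnormal and a patient-level count or shift. Vital signs have neither, although the other two parts of the same endpoint do.

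The drug is inhaled, and the stated purpose of protocol Amendment 3 is to help prevent possible bronchospasm after dosing. An acute change in respiratory rate, heart rate, blood pressure or oxygen saturation may affect only a few patients. It may also be recorded at an unscheduled contact, and those readings are left out of the by-visit tables. With efficacy reduced to descriptive summaries after early termination (SAP 3.3), safety carries much of what the trial can still report.

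**Working it through.** No figure in the documents applies to this endpoint, so the check traces each part of it to its planned output.

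| Part of the endpoint | Patient-level abnormality output in the SAP | Unscheduled results counted in it? |
|---|---|---|
| Laboratory (SAP 3.4.3) | Number and percent of patients in confirmed ALT/AST and platelet categories | Yes, by the SAP 3.1.1 rule |
| ECG (SAP 3.4.6) | Counts of overall interpretation; QTcF/QTcB shift to worst post-baseline value; patients with increases above 30 and 60 msec | Yes for the shift, by the same rule |
| Vital signs (SAP 3.4.4) | None | No such table exists |

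Protocol 10.6.2 has the same gap. It has vital signs and ECG tabulated by group and plans a count of patients with abnormalities for laboratory evaluations only.

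**Unscheduled readings.** The SAP 3.4.4 tables are by visit, so the exclusion applies to them. The exceptions are baseline, laboratory abnormality summaries and shift analyses. No shift analysis of vital signs is planned, so an unscheduled post-baseline vital sign reaches the listing and no vital-sign table.

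**What the by-visit statistics leave open.** The 59 dosed patients were allocated 2:2:1:1. With the placebos pooled this is 2:2:2, so 59/3 = 19.7, about 20 per group if actual allocation followed the ratio. As an illustration, take 20 patients attending each of three visits, with the group maximum above some limit and the 75th percentile below it every time.
- Fewest patients affected: the same one at all three visits, 1/20 = 5%.
- Most patients affected: at most 5 values lie above the 75th percentile at each visit. If these are different patients each time, 3 × 5 = 15, and 15/20 = 75%.

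Both cases fit that pattern of maxima and quartiles. The planned tables therefore do not determine the number of patients with an abnormal value.

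**Post-dose readings.** In Appendix A, vital signs are scheduled before dosing and at 2 hours on Days 1 and 85, and before dosing only on Days 15, 29, 43 and 57. The SAP reports that 10 patients completed Week 14, so for most patients Day 1 is probably the only scheduled post-dose reading. SAP 3.1.1 gives spirometry separate post-dose rows and gives vital signs none. The documents do not say whether the pre-dose and 2-hour readings share a visit label. If they do, the averaging rule merges them, which also dampens the maximum.

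**The case against.** The strongest reply is that the plan shows more than the endpoint trace suggests, and much of it stands.

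- A reader might infer that only means are reported. The documents do not support this: median, quartiles, minimum and maximum are planned. A 40 mm Hg rise in one of 20 patients moves a group mean by 40/20 = 2 mm Hg, but that does not measure what is hidden. If it is the largest rise at a scheduled visit and is not averaged with another reading, it prints as the maximum change.
- A reader might infer that abnormal readings appear in no output. A scheduled extreme can appear in the range, and every reading is listed. A reading reported as an adverse event also reaches the adverse event tables (SAP 3.4.2).
- A reader might infer that a bronchospasm signal would be missed. SAP 3.3.1 tabulates patients and doses with an FEV1 fall above 20%, and spirometry is scheduled 1 and 2 hours after dosing on Days 1 and 57. No document says that unscheduled vital signs are the readings most likely to be abnormal.
- The SAP agrees with protocol 10.6.2, so no planned vital-sign analysis was dropped. The mismatch is between the endpoint and the analysis sections of both documents.

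These points reduce the importance of the gap without closing it. A range by visit gives no patient count. A listing is not a summary by treatment group. Adverse event tables serve a separate endpoint and depend on what the investigator reports.

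**Conclusion.** The point holds in a limited form, and it is minor. Followed as written, the plan produces no number of patients with abnormal vital signs, no worst value per patient, and no table containing an unscheduled post-baseline reading. Pulse oximetry, collected as a vital sign, has no place in the planned vital-sign summary.

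The gap is confined to one part of a three-part safety endpoint with no hypothesis test, and the range, listings and adverse event tables cover it in part. The reading that the trial cannot report vital-sign safety at all goes too far.

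The group size of about 20 assumes that actual allocation followed the ratio. The 5% to 75% range is an illustration under full attendance and estimates nothing about this trial. The conclusion about the missing count depends on neither, nor on how the Day 1 readings are labelled.

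**What to change.** In SAP 3.4.4, add one Safety Set table by treatment group with two parts:
1. The number and percent of patients with at least one post-baseline value outside reporting limits that are fixed in the SAP before group results are seen.
2. A shift from baseline to each patient's worst post-baseline value.

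Use all time points, including post-dose and unscheduled readings, without averaging, and include pulse oximetry. Keep the by-visit tables.

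The 160/100 mm Hg level in protocol 5.2 is an eligibility limit. It may serve as one reporting category for blood pressure, but nothing in the documents makes it an on-treatment rule.

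The cost is a paragraph of SAP text and one table from data already collected. The downside is that the sponsor must choose reporting limits for heart rate, respiratory rate, temperature and oxygen saturation, which the documents do not supply.
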